Tarsius Pharma, Ltd.
Clinical Protocol Tarsius 2020 Trial

Project: TRS01

Compound Number / Name: TRS01

Protocol Number: Tarsius 2020

Protocol Title: A Phase I/IIa Multicenter, Double-Masked, Randomized, Vehicle-controlled, Dose-ranging Study to Evaluate the Safety of TRS01 Eye Drops in Subjects with Post-surgical Inflammation.

Sponsor: Tarsius Pharma, Ltd.
[name]
[name]
[name]

Medical Monitor:

[REDACTED]
[REDACTED]
[REDACTED]
[REDACTED]

Issue Date: Original: 12November2019
Amendment 01: 06March2020

Approved:

11 March 2020

[REDACTED]
[REDACTED]
[REDACTED]
Date

Tarsius Pharma, Ltd.
Clinical Protocol Tarsius 2020 Trial
Investigator Signature Page

Project: TRS01

Compound Number / Name: TRS01

Protocol Number: Tarsius 2020

Protocol Title: A Phase I/IIa Multicenter, Double-Masked, Randomized, Vehicle-controlled, Dose-ranging Study to Evaluate the Safety of TRS01 Eye Drops in Subjects with Post-surgical Inflammation.

Sponsor: Tarsius Pharma, Ltd.
[name]
[name]
[name]

Issue Date: Original: 12November2019
Amendment 01: 06March2020

**Contact for Serious
Adverse Events:**

[REDACTED]

[REDACTED]

[REDACTED]

[REDACTED]

Investigator Name:

Investigator's Signature:

Date

SYNOPSIS

Sponsor	Tarsius Pharma Ltd.
Study Title	A Phase I/IIa Multicenter, Double-Masked, Randomized, Vehicle-controlled, Dose-ranging Study to Evaluate the Safety of TRS01 Eye Drops in Subjects with Post-surgical Inflammation.
Study Objective	The primary objective of the study is to investigate the safety of TRS01 [REDACTED] (w/v) eye drops compared to vehicle in subjects who have undergone cataract surgery.
Study Population	The study population will consist of male and female subjects, aged 18 or older, who have undergone routine uncomplicated cataract surgery and experience \geq grade 2 threshold level of ocular inflammation 1 day post-operatively.
Number of Subjects	Approximately 60 subjects that meet the selection criteria will be randomized for treatment following cataract surgery (one study eye). The number of subjects that will be screened to obtain 60 randomized subjects is estimated at approximately 100 subjects.
Investigational Product	TRS01-[REDACTED], TRS01-[REDACTED], and TRS01-[REDACTED] eye drops, or vehicle, will be supplied as investigational product.
Route and duration of administration	Study subjects will administer the randomly assigned treatment, as eye drops, four times a day (QID) for 2 weeks.
Study Design	
A Phase I/IIa multicenter, double-masked, randomized, vehicle-controlled, dose-ranging study designed to evaluate the safety and preliminary efficacy of TRS01 eye drops ([REDACTED] compared to vehicle in subjects with post-surgical inflammation. Potential study participants will be asked to sign an informed consent document before the surgery and have to meet all preoperative inclusion/exclusion criteria. Following cataract surgery, subjects who are observed to have anterior chamber cells \geq grade 2 in the study eye on the Day 1 post-operative visit following a routine, uncomplicated cataract surgery will be eligible to be randomized to treatment (subjects who have $<$ grade 2 anterior chamber cells must be screen failed). Once it is determined that all eligibility criteria have been met, subjects will be enrolled and treated with one of three concentrations of TRS01 or vehicle in a 1:1:1:1 ratio. Approximately 60 eligible subjects will be enrolled in approximately five centers located in the United States (US) and France.
 
Study subjects will administer the randomly assigned treatment four times a day (QID) for 14 (± 1) days. All study subjects will return for examination on day 3, day 8 and day 15 post surgery. Day 15 visit will be

	
one day after the last day of treatment.
 
Clinical assessments will include subject-rated ocular pain assessment, slit lamp biomicroscopy, dilated ophthalmoscopy, intraocular pressure (IOP) measurement, snellen distance visual acuity (VA) by Pinhole Method.
 
[REDACTED]
 
[REDACTED]
 
The study visits schedule and assessments to be performed are described in Appendix 1.

Primary Safety Endpoints	
Assessment of ocular AEs: Changes that are expected due to uncomplicated cataract surgery will not be classified as AEs but will be recorded. AEs will be captured by verbatim term and coded using MedDRA.
 
Relevant clinical findings will also be recorded in the electronic case report form (eCRF) related to the following:
 
 1. Snellen distance VA by pinhole method 2. Slit lamp biomicroscopy 3. IOP measurement 4. Dilated ophthalmoscopy 5. Safety parameters include a change from baseline (1-day post-surgery) to each post-surgery visit in ocular signs such as: 
 o Conjunctival hyperemia o Corneal edema
Exploratory Efficacy Measurements	
 • Anterior chamber cell count on slit lamp biomicroscopy. At select sites. [REDACTED] • Anterior chamber flare assessed on slit lamp biomicroscopy • PROs-Subject-rated ocular pain assessment
Eligibility Criteria	
Inclusion Criteria
 
Pre-operatively, individuals of either gender or any race will be eligible for study participation if they are:
 
 1. 18 years of age or older. 2. Able to provide informed consent, follow instructions and complete all required study visits for the duration of the study. 3. Scheduled for routine cataract surgery (phacoemulsification or extracapsular extraction) with posterior chamber intraocular lens (IOL) implantation, and not combined with any other surgery.

	
 4. Have vision \geq 20/200 in the non-study eye. 5. Able to self-administer eye drops (tested during screening by self-administration of “artificial tears”), or have a care provider that can administer the drops. 6. Have no known sensitivity /allergy to the TRS01 or formulation excipients as detailed in TABLE 2 and TABLE 3. 7. Using adequate birth control by men and women, if of reproductive potential and sexually active. Adequate birth control is defined as agreement to consistently practice an effective and accepted method of contraception throughout the duration of the study and for 2 weeks after the last dose of investigational product. 
 a. For females, adequate birth control methods will be defined as hormonal contraceptives, intrauterine device or double barrier contraception, i.e., condom + diaphragm, condom or diaphragm + spermicidal gel or foam. b. For males, adequate birth control methods will be defined as double barrier contraception, i.e., condom + diaphragm, condom or diaphragm + spermicidal gel or foam. c. For females, menopause is defined as one year without menses; if in question, a follicle-stimulating hormone of >40 IU/L must be documented. Hysterectomy, bilateral oophorectomy, or bilateral tubal ligation must be documented, as applicable.
--	--

Exclusion Criteria

In order for subject to be eligible at Visit 1 they may not:

1. Be scheduled to undergo cataract surgery in the non-study eye for 2 months prior to Visit 1 and during the study.
2. Require use of any topical ophthalmic medications (either eye) other than study required medications for 14 days prior to surgery and for the duration of the trial. Note: Use of PRN artificial tears up to twice a day is allowed and should not be dosed within 10 minutes of investigational product dosing.
3. Require topical ocular therapy (either eye) with antibiotics for 30 days prior to surgery except antibiotic eye drops used as part of the Investigator’s routine pre-op, intra-op, and post-op routine care.
4. Require treatment with systemic NSAIDs, within 14 days prior to the surgery and for the duration of the trial. Occasional use (≤ 2 times per week) of NSAIDs or over the counter (OTC) painkillers

	
to treat minor non-ocular conditions is acceptable. Low-dose aspirin (81 mg) for cardiovascular prophylaxis is allowed. Acetaminophen is the preferred treatment for post-op pain on the day of surgery.
 
 5. Require treatment with systemic or ocular immunosuppressants or immunomodulators including systemic steroids (oral, inhaled, injectable, nasal, topical dermal) or alpha-1 antagonists for 30 days prior to surgery and for the duration of the trial. 6. Use any ocular, topical or systemic medication that could interfere with wound healing, the test agent, or the interpretation of study results, within 30 days prior to the day of surgery and for the duration of the trial. 7. Use of contact lenses in the study eye are prohibited for the duration of the study. 8. Have history of glaucoma surgery or any incisional ocular surgery in the study eye. History of uncomplicated refractive surgery 3 years prior to the cataract surgery is acceptable. 9. Have any significant ocular disease in the study eye in addition to the cataract that may confound the trial results per the Investigator's judgement. 10. Have proliferative diabetic retinopathy (PDR), not stable for at least one year in the study eye. 11. Currently being treated for wet macular degeneration. 12. Have current or history of herpes keratitis in the study eye. 13. Be diagnosed with Fuchs Corneal Dystrophy (FCD). 14. Have current or history of prior ocular inflammation in the study eye not related to prior allowed surgical procedure. 15. In the opinion of the Investigator, have current clinically significant dry eye requiring therapy of greater than twice a day (BID) eye drops in the study eye. Use of PRN artificial tears up to twice a day is allowed and should not be dosed within 10 minutes of investigational product dosing. 16. Use any Cannabidiol products during the trial. 17. Have history of glaucoma or uncontrolled IOP >22mmHg in the study eye on the day of screening. 18. Have floppy iris syndrome noted for the contralateral eye prior to surgery in the study eye. 19. Have any clinically significant systemic disease or condition (e.g.
--	--

	
hematological diseases) that, in the Investigator's opinion, may confound the trial results, pose a safety risk to the subject or preclude the subject from adhering to the protocol or completing the trial per protocol and instilling eye drops.
 
20. Have a known history of alcohol and/or drug abuse.
 
21. Be an employee of the site that is directly involved in the management, administration, or support of this study or be an immediate family member of the same.
 
22. Have been exposed to an investigational drug or investigational medical device within 60 days prior to Visit 1.
 
23. Be pregnant or lactating.

--	--

Randomization Inclusion Criteria (Visit 3/Day 1)

To qualify for randomization at the Day 1 (Visit 3), a subject must:

1. Have undergone routine, uncomplicated cataract surgery (phacoemulsification or extracapsular extraction) with posterior chamber IOL implantation, not combined with any other surgery (including but not limited to use of iris retractors, capsular fixation ring or anterior capsule staining with dye). Specifically, have NOT had any cataract surgery complication such as a posterior capsular rupture, vitreous loss or significant iris damage.
2. Have an IOP of ≤ 30 mmHg. Notes: Fluid release from the anterior chamber through the surgical incision is allowed (manual burping). The final IOP post release of fluid must be ≤ 30 mmHg and will be recorded as the visit IOP value. Use of IOP lowering medications are allowed beginning on Day 0, with the exception of prostaglandins. IOP lowering eye drops should be dosed at least 30 minutes before investigational product dosing.
3. Have anterior chamber cells \geq grade 2.
4. Continue to meet inclusion/exclusion criteria with respect to current ocular and medical conditions and must not be taking prohibited medications (section 6.4).

TABLE OF CONTENTS

1	Introduction.....	13
1.1	Description of Investigational Product.....	14
1.2	GCP Compliance.....	17
1.3	Study Population	17
2	Study Objectives.....	18
3	Study Design.....	19
3.1	Safety Endpoints	19
3.2	Exploratory Efficacy Endpoints	19
3.3	Description of the Study Design	19
3.3.1	Investigational product kit	21
3.3.2	Treatments administered.....	21
3.3.3	Method to minimize bias	22
4	Selection of Study Population	23
4.1	Subject Inclusion Criteria.....	23
4.2	Subject Exclusion Criteria.....	23
4.3	Randomization Inclusion Criteria	25
4.3.1	Masking and Randomization Methodology	26
4.4	Informed Consent.....	26

GCP	Good Clinical Practice
ICF	Informed Consent Form
ICH	International Conference on Harmonization
IEC	Independent Ethics Committee
IOL	Intraocular lens
IOP	Intraocular Pressure
IP	Investigational Product
IRB	Institutional Review Board
IWRS	Interactive Web Response System
ITT	Intent-to-Treat
LDPE	Low-density polyethylene
NSAIDs	Non-steroidal Anti-inflammatory Drugs
OD	Oculus Dexter (right eye)
OS	Oculus Sinister (left eye)
OTC	Over the counter
OU	Oculus Uterque (both eyes)
PP	Polypropylene
PP	Per Protocol
QID	Four times daily
SAE	Serious Adverse Event
SAR	Suspected Adverse Reaction
██████████	██████████
US	United States of America
VA	Visual Acuity
w/v	Weight to Volume

1 INTRODUCTION

Intraocular inflammation is a typical undesirable consequence of intraocular surgery such as cataract surgery. It is manifested principally as conjunctival injection, corneal edema, ciliary flush and aqueous cells and flare. Surgical trauma and phacoemulsification energy activate an inflammatory cascade that ultimately leads to formation of prostaglandins, which results in local vasodilation and increased vascular permeability.

Inflammation may resolve with no treatment in 15-28% of patients. However, inadequately treated inflammation after cataract surgery frequently causes pain, photophobia, increased risk for elevated intraocular pressure (IOP), corneal edema, corneal scarring and cystoid macular edema [Aptel et al., 2017]. Thus, managing and treating postoperative inflammation is an important goal following cataract surgery.

Other ocular inflammatory diseases include, for example, non-infectious uveitis, a potentially blinding condition that is the fifth leading cause of visual loss in the developed world (third leading cause of preventable blindness), has been estimated to account for 10% of all visual impairment in the western world and 10–15% of cases of total blindness [Nussenblatt, 1990; Merida et al., 2015]. Anterior uveitis accounts for approximately 80% of non-infectious uveitis cases in the United States [Thorne et al., 2016].

Uveitis is characterized by an inflammatory process that may be acute, recurrent, chronic or acute-on-chronic. Untreated, recurrent bouts of uveitis eventually lead to tissue destruction from direct inflammation or from complications such as cataract, glaucoma and macular edema.

Topical corticosteroids represent first line treatment for both non-infectious uveitis and postoperative inflammation. In the US, topical corticosteroids are routinely prescribed with four times daily (QID) dosing for at least 2 weeks following cataract surgery [Kim et al., 2019].

The side effects associated with steroid use, significantly limit prolonged treatment. The most common adverse effects of ocular steroids are cataract and elevated IOP which can lead to steroid related glaucoma.

Given the limitations of treatment, there is a need for an effective anti-inflammatory drug that does not have an IOP-elevating effect. Tarsius Pharma has developed a novel therapeutic approach for local prevention and treatment of ophthalmic inflammatory diseases. [REDACTED]

[REDACTED]

[REDACTED]

[REDACTED]

[REDACTED]

[REDACTED]

[REDACTED]

[REDACTED]

[REDACTED]

The Tarsius-2020-Trial is a Phase I/IIa multicenter, double-masked, randomized, vehicle-controlled, dose-ranging (3 doses – [REDACTED] study to evaluate the safety and preliminary efficacy of TRS01 eye drops in subjects with post-surgical inflammation.

1.1 DESCRIPTION OF INVESTIGATIONAL PRODUCT

TRS01 is formulated as a sterile ophthalmic solution of TRS drug substance in a vehicle composed of [REDACTED]

[REDACTED]. For this trial, dosing volume and dose delivery of TRS01 investigational product (IP) will be supplied as summarized in **TABLE 1**.

[REDACTED]. The vehicle control contains the same excipients as TRS01, without the Active Pharmaceutical Ingredient.

TABLE 1: TRS01 AND VEHICLE DOSING VOLUME AND DOSE DELIVERY

	Eye Drop Volume of:	Will deliver approximately:
TRS01 Low Dose	[REDACTED]	[REDACTED]
TRS01 Medium Dose	[REDACTED]	[REDACTED]
TRS01 High Dose	[REDACTED]	[REDACTED]
TRS01 Vehicle	[REDACTED]	[REDACTED]

Corresponding matching vehicle will also be prepared for use in the planned clinical trial, to ensure masking of the clinical trial. Subjects randomized to the vehicle-control arm will receive the same bottles containing all excipients at the same concentrations used in TRS01 solutions with exception of TRS itself (the active ingredient).

The IP will be packaged and labeled by [REDACTED] in accordance with current Good Manufacturing Practices as appropriate for clinical supplies and applicable national laws. Study medications will be clearly labeled as to contents and storage conditions. A caution statement will be printed on the label, along with the name and address of Tarsius Pharma.

[REDACTED]

[REDACTED]

[REDACTED]

[REDACTED]

[REDACTED]

[REDACTED]

Subjects are expected to self-administer, or have a care provider administer, one drop four times per day (QID) of TRS01-[REDACTED], TRS01-[REDACTED], TRS01-[REDACTED] or vehicle control.

Double-masked doses will be assigned through the randomization program. The treatment schedule is shown in FIGURE 1. TRS01 will be administered no more frequently than four times daily (QID) per protocol.

TABLE 2: COMPOSITION OF TRS01 [REDACTED] INVESTIGATIONAL PRODUCT

Ingredient	Ingredient name According to USP	Function	Concentration (%w/v)		
			[REDACTED]	[REDACTED]	[REDACTED]
[REDACTED]		[REDACTED]	[REDACTED]	[REDACTED]	[REDACTED]
[REDACTED]	[REDACTED]	[REDACTED]	[REDACTED]	[REDACTED]	[REDACTED]
[REDACTED]	[REDACTED]	[REDACTED]	[REDACTED]	[REDACTED]	[REDACTED]
[REDACTED]	[REDACTED]	[REDACTED]	[REDACTED]	[REDACTED]	[REDACTED]
[REDACTED]	[REDACTED]	[REDACTED]	[REDACTED]	[REDACTED]	[REDACTED]
[REDACTED]	[REDACTED]	[REDACTED]	[REDACTED]	[REDACTED]	[REDACTED]
[REDACTED]	[REDACTED]	[REDACTED]	[REDACTED]	[REDACTED]	[REDACTED]
Wa[REDACTED]	[REDACTED]	[REDACTED]	[REDACTED]	[REDACTED]	[REDACTED]

TABLE 3: COMPOSITION OF VEHICLE

Ingredient	Ingredient name According to USP	Function	TRS01-Vehicle (%w/v)
[REDACTED]	[REDACTED]	[REDACTED]	[REDACTED]
[REDACTED]	[REDACTED]	[REDACTED]	[REDACTED]
[REDACTED]	[REDACTED]	[REDACTED]	[REDACTED]
[REDACTED]	[REDACTED]	[REDACTED]	[REDACTED]
[REDACTED]	[REDACTED]	[REDACTED]	[REDACTED]
[REDACTED]	[REDACTED]	[REDACTED]	[REDACTED]
[REDACTED]	[REDACTED]	[REDACTED]	[REDACTED]
[REDACTED]	[REDACTED]	[REDACTED]	[REDACTED]
[REDACTED]	[REDACTED]	[REDACTED]	[REDACTED]

1.2 GCP COMPLIANCE

The study will be conducted in accordance with the study protocol, Good Clinical Practice (GCP), International Conference on Harmonization (ICH) of technical requirements for registration of pharmaceuticals for human use guidelines. Compliance with these requirements is consistent with the ethical principles that have their origins in the Declaration of Helsinki (Declaration of Helsinki, 2013).

1.3 STUDY POPULATION

The study population will consist of male and female subjects, aged 18 or older, who have undergone routine uncomplicated cataract surgery and experience ocular inflammation on the Day 1 post-surgery visit. Approximately 100 subjects who are candidates for cataract surgery will be screened and approximately 60 subjects with anterior chamber cells \geq grade 2 will be randomized to one of four groups, i.e., three treatment groups or vehicle. Only the study eye (surgery eye) of each subject will be treated with IP.

2 STUDY OBJECTIVES

The primary objective of this study is to evaluate the safety of TRS01 eye drops at concentrations of [REDACTED] w/v) compared to vehicle in subjects who have undergone uncomplicated cataract surgery.

The exploratory objective of the study is to assess the preliminary efficacy of TRS01 eye drops in reducing inflammation as compared to vehicle.

3 STUDY DESIGN

This is a phase I/IIa multicenter, double-masked, randomized, vehicle-controlled, dose-ranging study.

It is designed to evaluate the safety and preliminary efficacy of TRS01 eye drops (████████) compared to vehicle in subjects with post-surgical inflammation.

3.1 SAFETY ENDPOINTS

The primary safety parameter in this study is the incidence and severity of treatment-emergent and treatment-related adverse events (AEs), both systemic and ocular events in subjects with post-cataract inflammation. Changes that are expected due to uncomplicated cataract surgery will not be classified as AEs but will be recorded.

1. Snellen distance visual acuity (VA) by pinhole method
2. Slit lamp biomicroscopy
3. IOP measurement
4. Dilated ophthalmoscopy
5. Change from baseline (1-day post-surgery) to each post-surgery visit in ocular signs:
 - Conjunctival hyperemia
 - Corneal Edema

All Relevant clinical findings will be recorded in the electronic case report form (eCRF).

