3.3 DESCRIPTION OF THE STUDY DESIGN

This is a Phase I/IIa Multicenter, Double-Masked, Randomized, Vehicle-Controlled, Dose-ranging study designed to evaluate the safety and preliminary efficacy of TRS01 eye drops at three dose levels compared to vehicle in subjects with post-surgical inflammation.

Approximately 60 subjects with ocular inflammation following cataract surgery will be randomized at approximately five centers, in the USA and in France.

Subjects who provide informed consent and meet all study randomization criteria will be enrolled in the study and randomized in a 1:1:1:1 ratio to receive TRS01-█%, TRS01-█, TRS01-█% or vehicle eye drops four times daily.

The eye that underwent cataract surgery is defined as the study eye. TRS01 should not be administered in the fellow eye.

Treatment assignments will be masked to Tarsius, study subjects, Investigators, and site staff. In order to prevent unmasking, all study medications during the Treatment Period will be supplied in identical packages.

The study design includes 14-days of a double-masked treatment period, with the endpoint assessment conducted on Day 15 (FIGURE 1 summarizes the study phases, anticipated visits and number of subjects at each phase and Appendix 1 summarizes the schedule of assessments from Screening through Day 15).

Randomization is employed as an unbiased method of assigning subjects to four groups in equal allocation.

Male and female subjects aged 18 or older and 1-day post cataract surgery with anterior chamber cells \geq grade 2 in the study eye, are eligible to be randomized to participate in the treatment phase of the study.

[figure not shown]
Double-masked eye drops will be administered four times daily from Day 1 through Day 14 by the study participant (or care provider) to the study eye. The safety endpoint is on Day 15. Exploratory efficacy measurements will be collected.

Visits (including the surgery day):

1. Visit 1/Days -30 to -1 – Screening: Initial screening for eligibility – 1-30 days before the surgery.
2. Visit 2/Day 0 – Surgery: Eligible subjects will undergo routine cataract surgery according to investigator's standard procedures. No steroid or NSAID will be given before, during or after the surgery. Acetaminophen on the day of surgery is allowed.

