7 SAFETY AND EFFICACY VARIABLES

7.1 SAFETY VARIABLE

Incidence and severity of treatment-related AEs and SAEs, both systemic and ocular events.

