7.2.1 Adverse Events

Adverse events will be collected for subjects following signing of the ICF through the end of the study. The information will include at least a description of the event, onset date, and resolution date, as well as seriousness, severity and relation to study medication (as determined by the Investigator), location (right eye [OD], left eye [OS], both eyes [OU] or other), action taken, and outcome. All AEs will be coded using the Medical Dictionary for Regulatory Activities (MedDRA) dictionary, current version. Ocular and non-ocular AEs will be summarized separately.

Suspected adverse reactions (SARs), also known as adverse drug reactions or suspected adverse drug reactions, are AEs considered by the Investigator to be related to the study medication and included in the Investigator's Brochure.

An AE will be considered as an *ocular AE* if the Investigator selects 'OD', 'OS', or 'OU' for the AE eCRF field "Eye(s) affected".

Any AE that causes loss of vision of 15 or more letters (i.e., 3 lines) should be recorded as a serious adverse event (SAE). Examples include endophthalmitis, retinal vascular occlusion, retinal detachment involving the macula/fovea, etc. AEs that cause loss of 15 or more letters (i.e., 3 lines) that are expected to resolve should not be recorded as an SAE. Examples include corneal edema, corneal abrasion, cystoid macular edema or other conditions that are known to affect vision but expected to resolve and not results in a permanent impact on vision.

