9.1.2 Analysis of Safety

Analysis of safety data will be presented for all subjects. AEs will be coded using Medical Dictionary for Regulatory Activities (MedDRA, most current version) and categorized by system organ class using preferred terms. Treatment emergent AEs will be listed by study group. Treatment related AEs will be tabulated by study group and will be reported by incidence (both number of events and number of subjects) with respect to their intensity and relationship to the IP. Ophthalmoscopy findings will be summarized descriptively. IOP measurements, VA, and slit lamp biomicroscopy will be summarized as safety outcomes.

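### The synopsis and section 3.1 name different primary safety outcomes, and section 9.1.2 plans no incidence table for treatment-emergent AEs

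*Combined protocol and SAP*

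**What the plan says.** Section 2 makes safety compared with vehicle the primary objective. The outcome that measures it is described in several places.

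- **Synopsis, primary safety endpoints row:** "Assessment of ocular AEs: Changes that are expected due to uncomplicated cataract surgery will not be classified as AEs but will be recorded". It mentions neither systemic events nor incidence or severity, and does not say whether events must be treatment-emergent or related.
- **Section 3.1:** "The primary safety parameter in this study is the incidence and severity of treatment-emergent and treatment-related adverse events (AEs), both systemic and ocular events".
- **Section 7.1**, headed as the safety variable but not called primary: "Incidence and severity of treatment-related AEs and SAEs, both systemic and ocular events".
- **Section 9.1.2 (analysis):** "Treatment emergent AEs will be listed by study group", whereas "Treatment related AEs will be tabulated by study group and will be reported by incidence", counting both events and subjects. No analysis is called primary.
- **Section 7.2.1:** "Ocular and non-ocular AEs will be summarized separately". Neither group is named as primary. AEs are collected from consent to study end.
- **Section 3.3:** "The safety endpoint is on Day 15".

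Sections 9.1 and 9.3 defer to a Statistical Analysis Plan. The supplied text contains the protocol only, so whether that plan settles the definition cannot be checked.

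**The concern.** A trial whose primary objective is safety should identify one set of events as its primary result before unmasking. Here the synopsis and section 3.1 both use the word primary and describe different sets. A report that followed the synopsis would lead with ocular events. One that followed 3.1 would lead with ocular and systemic events together.

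The causality qualifier matters as well. Section 7.3 offers three levels (unrelated, probable, definite), with none for a possible relationship, and assigns to unrelated any event that the surgery readily accounts for. A count of related events can therefore be much smaller than a count of all treatment-emergent events, and it rests on the investigator's judgement. If 3.1 is meant to include all treatment-emergent events, section 9.1.2 does not plan the incidence table that would report them.

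**Working it through.** **Step 1. The definitions side by side**

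| Place | Called primary? | Body system | Treatment-emergent | Related | Metric |
|---|---|---|---|---|---|
| Synopsis | Yes | Ocular only | Not stated | Not stated | None |
| 3.1 | Yes | Ocular and systemic | Yes | Yes | Incidence, severity |
| 7.1 | No | Ocular and systemic | Not stated | Yes, with SAEs added | Incidence, severity |
| 9.1.2 | No | Not stated | Listing only | Incidence table | Events and subjects |

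The synopsis and 3.1 conflict on any reading, because one includes systemic events and the other omits them. The synopsis also sets no start point. Since collection begins at consent (7.2.1), its wording does not exclude events before the first dose.

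**Step 2. Does 7.1 differ from 3.1?** This depends on how 3.1 is read.

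- *Both conditions at once.* Section 7.3 classes events before dosing as unrelated, so every related event is also treatment-emergent. Section 3.1 then reduces to related AEs. It nearly matches 7.1, provided that the word related in 7.1 also governs SAEs.
- *Two categories.* Section 3.1 then covers all treatment-emergent AEs, with related AEs also reported, and is wider than 7.1.

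Section 9.1.2 handles the two as separate categories, which favours the second reading without proving it.

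**Step 3. Possible size.** The protocol gives no AE rates and section 9.2 is redacted, so there is no plan figure to reproduce. The following is an illustration.

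Inputs from the protocol: about 60 subjects randomized 1:1:1:1, so 60/4 = 15 per arm.

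Assumed inputs: probability that a subject has an ocular AE (po), probability of a systemic AE (ps), the two independent, and share judged related (r). All events are taken to start after the first dose.

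- Any ocular AE: po
- Any treatment-emergent AE: 1 − (1 − po)(1 − ps)
- Any related AE: 1 − (1 − po·r)(1 − ps·r)

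First row worked out: 1 − 0.80 × 0.90 = 28%; 1 − 0.95 × 0.975 = 7.4%. Multiplying by 15 gives 3.0, 4.2 and 1.1 subjects.

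| po / ps / r (assumed) | Any ocular (synopsis) | Any treatment-emergent (3.1 as two categories) | Related only (7.1, or 3.1 as one joint condition) |
|---|---|---|---|
| 20% / 10% / 25% | 20% (3.0) | 28% (4.2) | 7.4% (1.1) |
| 30% / 15% / 50% | 30% (4.5) | 40.5% (6.1) | 21.4% (3.2) |
| 40% / 20% / 25% | 40% (6.0) | 52% (7.8) | 14.5% (2.2) |
| 20% / 10% / 75% | 20% (3.0) | 28% (4.2) | 21.4% (3.2) |

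Expected subjects per arm are in brackets. If 7.1 also counts SAEs regardless of causality, an assumed independent 2% SAE rate moves 7.4% to 1 − 0.926 × 0.98 = 9.2%, and 14.5% to 1 − 0.855 × 0.98 = 16.2%.

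**The case against.** The strongest reply is that little is lost in practice. AEs of every location are collected, ocular and non-ocular events are to be summarized separately, all study data are to be listed, and incidence of related AEs is already committed. The supplied text gives no safety test, success threshold or significance level. On that view only emphasis in the report is at stake, and the Statistical Analysis Plan may settle it.

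Much of this stands, and it rules out several stronger readings that a reader might infer:

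- *Three incompatible primary endpoints.* Section 7.1 is not labelled primary and nearly matches 3.1 on one fair reading.
- *The synopsis means ocular AEs of any cause.* The synopsis is silent on causality. That wording would have to be supplied by the reader.
- *Systemic events are dropped from the trial.* Only the synopsis label omits them; collection and summary do not.
- *Only Day 15 events count.* Section 3.3 also places the endpoint assessment on that day, and Appendix 1 has AEs assessed at every visit. The natural reading is that assessment ends on Day 15.

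The reply does not remove the core conflict. Two passages label the primary outcome and disagree. The summary promised in 7.2.1 does not say which AEs or which measure it covers, and 9.1.2 gives treatment-emergent AEs a listing only. A Statistical Analysis Plan could choose one version, but the protocol would still contradict itself.

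**Conclusion.** The point holds as an internal inconsistency. The disagreement between the synopsis and 3.1 is firm and needs no assumption. The difference between 3.1 and 7.1 depends on reading 3.1 as two categories, which 9.1.2 supports. The missing incidence table for treatment-emergent AEs follows from 9.1.2 as written, subject to whatever the unseen Statistical Analysis Plan adds.

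The consequence is uncertainty over which incidence is presented as primary. A reader might go further and infer inflated error or a free choice of a successful result. The documents do not support that, because the planned safety analysis is descriptive and has no success criterion.

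The size cannot be fixed from the documents. In the illustrations the related-only rate runs from under a third of the treatment-emergent rate (14.5% against 52%) to about three quarters of it (21.4% against 28%). The ocular and related-only rates almost coincide when 75% of events are judged related. The discrepancy in wording remains whatever the rates. Because it concerns the trial's primary outcome and is cheap to correct, it should be corrected.

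**What to change.** Adopt one definition and use it in the synopsis, 3.1, 7.1 and 9.1.2. The documents require consistency; the choice of event set is the sponsor's. One workable version: the number and percent of subjects with at least one treatment-emergent AE, meaning onset from first dose to study end, by severity and arm, with ocular and non-ocular events shown separately and treatment-related AEs and SAEs reported as subsets. This stays within the collection window of 7.2.1.

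In 9.1.2, replace the listing of treatment-emergent AEs with a tabulation of their incidence (the listing can stay as a supplement), and label that table as the primary safety analysis. Bring the Statistical Analysis Plan into line. Optionally, state that the Day 15 sentence in 3.3 refers to the final examination.

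The cost is wording in four sections, a further sentence if 3.3 is clarified, and one added table. No new data are needed: 7.2.1 already provides for onset date, severity, seriousness, causality and location of each event.
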